### **ECG data**

The analysis of ECG parameters will be performed as described in chapter 6.2 with the Safety Analysis Set. The listing will also include linked AE verbatim(s) and medical history verbatim(s).

### **Further safety endpoints**

Childbearing Status / Pregnancy test data and virology data will be listed only.

## 7.6 Further Analyses

If not stated otherwise, all further analyses will be performed as described in chapter 6.2 with the Safety Analysis Set.

### Previous and concomitant medication

The incidence of previous and concomitant medication will be displayed by ATC (Anatomical Therapeutic Chemical) classification (level 1 and 2 and preferred term). The analysis will be performed separately for previous medications and concomitant medications for the Safety Analysis Set. The listing will include a flag indicating if a medication is P (Previous) or C (Concomitant) or PC.

### Study medication

- Duration of intake of study medication [days]
- Number of capsules dispense

will be analysed as described in chapter 6.2 with the Safety Analysis Set.

### Termination status at end of trial

The incidence and reason for premature study termination (Screening failure, AE, Patient decision (withdrawal of consent to participate), Investigator discretion, Patient lost to follow-up, Lack of efficacy, Pregnancy, Other reasons) will be analysed for the Enrolled Set, i.e. including screening failures and randomised patients, and Safety Analysis Set.

Patients discontinued prematurely will be listed.

The incidence and reason (Violation of Inclusion Criteria X, Violation of Exclusion Criteria Y, Other) for Screening failure will be summarised (using non-randomised subjects of the Enrolled Set only).

### Study duration and analysis sets

The day of first patient in the study and last patient out of the study will be given for the Enrolled Set as well as for the Safety Analysis Set.

The number of patients in each analysis set will be given by centre and overall. All patients will be listed with their assignment to the analysis populations and if applicable the reason for exclusion from specific analysis sets.

### Protocol violations

Protocol violations identified in the BDRM will be listed including the decision if these constitute a minor or major protocol violation.

## 8 Tables and Figures

Item No.	Title	Population	Content Description	Mock Table
14.1.1	Patient disposition			
14.1.1.1	Patient disposition	Enrolled Set	Descriptive statistics of number of patients in analysis populations by centre and overall	T1
14.1.1.2	Study duration	Enrolled Set	Date of first patient in and last patient out	T2
14.1.1.2.1	Study duration	SAS	Date of first patient in and last patient out	T2
14.1.2	Demographic data			
14.1.2.1	Demographic data I	Randomised Set	Descriptive statistics of continuous variables	T3
14.1.2.2	Demographic data II	Randomised Set	Frequency table of categorical variables	T4
14.1.3	Medical history and baseline evaluation			
14.1.3.1	Medical history / Concomitant diseases by MedDRA primary SOC and preferred term	FAS	Frequency Table	T5
14.2	Efficacy			
14.2.1	Primary Endpoint			
	vIGA-AD™ score			
14.2.1.1	vIGA-AD™ score by visit	FAS	Frequency table by visit	T4a
14.2.1.2	vIGA-AD™ score by visit and subgroup	FAS	Frequency table by visit and subgroup	T4a
14.2.1.3	vIGA-AD™ response by visit	FAS	Descriptive statistics by visit	T4a
14.2.1.4	vIGA-AD™ response by visit and subgroup	FAS	Descriptive statistics by visit and subgroup	T4a
14.2.1.5	vIGA-AD™ score proportion from baseline to week 16 (GLMM)	FAS	Proportion (n (%)) of patients achieving an vIGA-AD™ score of 0 (clear) or 1 (almost clear) and a decrease of at least 2 points in vIGA-AD™ from baseline to Week 16 using a Generalised Linear Mixed Model	T6.1 T6.2

14.2.1.5.1	vIGA-AD™ score proportion from baseline to week 16 (GLMM)	PPS	Proportion of patients achieving an vIGA-AD™ score of 0 (clear) or 1 (almost clear) and a decrease of at least 2 points in vIGA-AD™ from baseline to Week 16 using a Generalised Linear Mixed Model	T6.1 T6.2
14.2.1.6	vIGA-AD™ score proportion from baseline to week 16 (GLMM) by subgroup	FAS	Proportion of patients achieving an vIGA-AD™ score of 0 (clear) or 1 (almost clear) and a decrease of at least 2 points in vIGA-AD™ from baseline to Week 16 using a Generalised Linear Mixed Model by subgroup	T6.1 T6.2
14.2.1.7	Sensitivity analysis of vIGA-AD™ score proportion from baseline to week 16 (de facto estimand)	FAS	Jump to reference method to estimate the de facto estimand	T7.1 T7.2
14.2.1.8	Sensitivity analysis of vIGA-AD™ score proportion from baseline to week 16 (rescue medication)	FAS	Patients who received rescue medication will be evaluated as treatment failures	T6.1 T6.2
EASI-75 score				
14.2.1.9	EASI score by visit	FAS	Descriptive statistics by visit	T3a
14.2.1.10	EASI score by visit and subgroup	FAS	Descriptive statistics by visit and subgroup	T3a
14.2.1.11	EASI-75 response by visit	FAS	Descriptive statistics by visit	T4a
14.2.1.12	EASI-75 response by visit and subgroup	FAS	Descriptive statistics by visit and subgroup	T4a
14.2.1.13	EASI-75 response from baseline to week 16 (GLMM)	FAS	Proportion of patients achieving EASI-75 ( $\geq 75\%$ improvement from baseline) at Week 16 using a Generalised Linear Mixed Model	T6.1 T6.2

14.2.1.13.1	EASI-75 response from baseline to week 16 (GLMM)	PPS	Proportion of patients achieving EASI-75 ( $\geq 75\%$ improvement from baseline) at Week 16 using a Generalised Linear Mixed Model	T6.1 T6.2
14.2.1.14	EASI-75 response from baseline to week 16 (GLMM) by subgroup	FAS	Proportion of patients achieving EASI-75 ( $\geq 75\%$ improvement from baseline) at Week 16 using a Generalised Linear Mixed Model by subgroup	T6.1 T6.2
14.2.1.15	Sensitivity analysis of EASI-75 response from baseline to week 16 (de facto estimand)	FAS	Jump to reference method to estimate the de facto estimand	T7.1 T7.2
14.2.1.16	Sensitivity analysis of EASI-75 response from baseline to week 16 (rescue medication)	FAS	Patients who received rescue medication will be evaluated as treatment failures	T6.1 T6.2
14.2.2	Secondary Endpoints			
14.2.2.1	vIGA-ADTM score			
14.2.2.1.1	vIGA-AD TM score proportion from baseline to week 4, 8, 12, 18, 20 (GLMM)	FAS	Proportion of patients achieving an vIGA-AD TM score of 0 (clear) or 1 (almost clear) and a decrease of at least 2 points in vIGA-AD TM from baseline to Week 4, 8, 12, 18 and 20 using a Generalised Linear Mixed Model	T6.1 T6.2
14.2.2.1.2	Change in vIGA-AD TM score proportion at follow-up (GLMM)	FAS	Change in proportion of patients achieving an vIGA-AD TM score of 0 (clear) or 1 (almost clear) and a decrease of at least 2 points in vIGA-AD TM from Week 16 to Week 18 and 20 using a Generalised Linear Mixed Model	T6.1 T6.2
14.2.2.1.3	Change in vIGA-AD TM score from baseline to week 4, 8, 12, 16, 18, 20 (MMRM)	FAS	Change in vIGA-AD TM score from baseline to week 4, 8, 12, 16, 18, 20 using Mixed Model with Repeated Measures	T8.1 T8.2

14.2.2.1.4	Change in vIGA-AD™ score at follow-up (MMRM)	FAS	Change in vIGA-AD™ score from week 16 to week 18 and 20 using Mixed Model with Repeated Measures	T8.1 T8.2
14.2.2.1.5	Change in vIGA-AD™ score (mixed ordinal logistic regression)	FAS	Change in vIGA-AD™ score using mixed ordinal logistic regression	T9.1 T9.2
14.2.2.2	EASI score			
14.2.2.2.1	EASI-75 proportion from baseline to week 4, 8, 12, 18, 20 (GLMM)	FAS	Proportion of patients achieving EASI-75 ( $\geq 75\%$ improvement from baseline) at Week 4, 8, 12, 18 and 20 using a Generalised Linear Mixed Model	T6.1 T6.2
14.2.2.2.2	Change in EASI score from baseline to week 4, 8, 12, 16, 18, 20 (MMRM)	FAS	Change in EASI score from baseline to week 4, 8, 12, 16, 18, 20 using Mixed Model with Repeated Measures	T8.1 T8.2
14.2.2.2.3	Change in EASI score at follow-up (MMRM)	FAS	Change in EASI score from week 16 to week 18 and 20 using Mixed Model with Repeated Measures	T8.1 T8.2
14.2.2.2.4	EASI-50 proportion from baseline to week 4, 8, 12, 16, 18, 20 (MMRM)	FAS	Proportion of patients achieving EASI-50 ( $\geq 50\%$ improvement from baseline) at Week 4, 8, 12, 18 and 20	T8.1 T8.2
14.2.2.2.5	Change in EASI score by visit	FAS	Descriptive statistics by visit	T3a
14.2.2.2.6	EASI-50 response by visit	FAS	Descriptive statistics by visit	T4a
14.2.2.3	NRS			
14.2.2.3.1	NRS 4 point decrease proportion (MMRM)	FAS	Proportion of patients achieving a decrease of at least 4 points in worst itch NRS from baseline to week 4, 8, 12, 16, 18, 20	T8.1 T8.2

14.2.2.3.2	NRS 3 point decrease proportion (MMRM)	FAS	Proportion of patients achieving a decrease of at least 3 points in worst itch NRS from baseline to week 4, 8, 12, 16, 18, 20	T8.1 T8.2
14.2.2.3.3	Change in NRS (MMRM)	FAS	Change from baseline in worst itch NRS to week 4, 8, 12, 16, 18, 20	T8.1 T8.2
14.2.2.3.4	Change in NRS at follow-up (MMRM)	FAS	Change from week 16 in worst itch NRS to week 18 and 20	T8.1 T8.2
14.2.2.3.5	NRS score by visit	FAS	Descriptive statistics by visit	T3a
14.2.2.3.6	Change in NRS score	FAS	Descriptive statistics	T3a
14.2.2.3.7	NRS 3 point decrease and NRS 4 point decrease	FAS	Descriptive statistics	T4a
14.2.2.4	BSA			
14.2.2.4.1	Change in BSA (MMRM)	FAS	Change from baseline in the body surface area affected by AD to week 4, 8, 12, 16, 18, 20	T8.1 T8.2
14.2.2.4.2	Change in BSA at follow-up (MMRM)	FAS	Change from week 16 in the body surface area affected by AD to week 18 and 20	T8.1 T8.2
14.2.2.4.3	Body Surface Area (Value, Change from Baseline, Change from Wk 16) by visit	FAS	Descriptive statistics of body surface area at baseline and week 4, 8, 12, 16, 18, 20	T3a
14.2.2.5	SCORAD score			
14.2.2.5.1	Change in SCORAD (MMRM)	FAS	Change from baseline in the SCORAD score to week 4, 8, 12, 16, 18, 20	T8.1 T8.2
14.2.2.5.2	Change in SCORAD at follow-up (MMRM)	FAS	Change from week 16 in the SCORAD score to week 18 and 20	T8.1 T8.2
14.2.2.5.3	SCORAD (Value, Change from Baseline, Change from Wk 16) by visit	FAS	Descriptive statistics by visit	T3a
14.2.2.6	Exploratory Endpoints			
	vIGA-AD™ score			

14.2.2.6.1	vIGA-AD™ score 2 point decrease proportion (MMRM)	FAS	Proportion of patients achieving a decrease of at least 2 points in vIGA-AD™ from baseline to Week 4, 8, 12, 16, 18 and 20	T8.1 T8.2
14.2.2.6.2	Change in vIGA-AD™ score 2 point decrease proportion at follow-up (MMRM)	FAS	Change in proportion of patients achieving a decrease of at least 2 points in vIGA-AD™ from Week 16 to Week 18 and 20	T8.1 T8.2
DLQI score				
14.2.2.6.3	Change in DLQI score (MMRM)	FAS	Change from baseline in the DLQI score to week 4, 8, 12, 16, 18, 20	T8.1 T8.2
14.2.2.6.4	Change in DLQI score at follow-up (MMRM)	FAS	Change from week 16 in the DLQI score to week 18 and 20	T8.1 T8.2
14.2.2.6.5	DLQI score (Value, Change from Baseline, Change from Wk 16) by visit	FAS	Descriptive statistics by visit	T3a
POEM score				
14.2.2.6.6	Change in POEM score (MMRM)	FAS	Change from baseline in the POEM score to week 4, 8, 12, 16, 18, 20	T8.1 T8.2
14.2.2.6.7	Change in POEM score at follow-up (MMRM)	FAS	Change from week 16 in the POEM score to week 18 and 20	T8.1 T8.2
14.2.2.6.8	POEM score (Value, Change from Baseline, Change from Wk 16) by visit	FAS	Descriptive statistics by visit	T3a
Athens Insomnia Scale				
14.2.2.6.9	Change in sleep quality assessment (MMRM)	FAS	Change from baseline in sleep quality assessment (Athens Insomnia Scale) to week 4, 8, 12, 16, 18, 20	T8.1 T8.2
14.2.2.6.10	Change in sleep quality assessment at follow-up (MMRM)	FAS	Change from week 16 in sleep quality assessment (Athens Insomnia Scale) to week 18 and 20	T8.1 T8.2

14.2.2.6.11	Sleep quality assessment (Value, Change from Baseline, Change from Wk 16) by visit	FAS	Descriptive statistics by visit	T3a
	PO-SCORAD Score			
14.2.2.6.12	Change in PO-SCORAD score (MMRM)	FAS	Change from baseline in PO-SCORAD score to week 4, 8, 12, 16, 18, 20	T8.1 T8.2
14.2.2.6.13	Change in PO-SCORAD score at follow-up (MMRM)	FAS	Change from week 16 in PO-SCORAD score to week 18 and 20	T8.1 T8.2
14.2.2.6.14	PO-SCORAD (Value, Change from Baseline, Change from Wk 16) by visit	FAS	Descriptive statistics by visit	T3a
14.2.3	Further Analyses			
14.2.3.1	Previous medication	SAS	Descriptive statistics by ATC classification (level 1 and 2 and preferred term)	T10
14.2.3.2	Concomitant medication	SAS	Descriptive statistics by ATC classification (level 1 and 2 and preferred term)	T10
14.2.3.3	Reason for Termination	Enrolled Set	Frequency Table	T4
14.2.3.3.1	Reason for Termination	SAS	Frequency Table	T4
14.2.3.4	Screening failure	Non-randomised subjects of the Enrolled Set	Frequency Table	T4
14.3	Safety			
14.3.1	Study medication			
14.3.1.1	DS107 intake duration	SAS	Descriptive statistics	T3
14.3.1.2	Capsules	SAS	Descriptive statistics of number of capsules dispensed	T3
14.3.2	Adverse events			
14.3.2.1	Summary table of Adverse Events	SAS	Frequency table of patients and number of events per AE category	T11
14.3.2.2	Adverse Events by MedDRA SOC and preferred term	SAS	Frequency table	T12

14.3.2.3	Serious Adverse Events by MedDRA SOC and preferred term	SAS	Frequency table	T12
14.3.2.4	AEs related to DS107 by MedDRA SOC and preferred term	SAS	Frequency table	T12
14.3.2.5	AEs leading to study discontinuation by MedDRA SOC and preferred term	SAS	Frequency table	T12
14.3.2.6	AEs by SOC, PT and worst intensity	SAS	Frequency table	T13
14.3.2.7	AEs by SOC, PT and outcome	SAS	Frequency table	T13
14.3.2.8	SAEs by SOC, PT and outcome	SAS	Frequency table	T13
14.3.2.9	Most frequent non-serious adverse events by MedDRA SOC and preferred term	SAS	Frequency table	T13
14.3.5	Vital signs			
14.3.5.1	Vital signs	SAS	Descriptive Statistics	T3a
14.3.5.2	Change in vital signs from baseline	SAS	Descriptive Statistics	T3a
14.3.5.3	ECG	SAS	Descriptive Statistics	T4a
14.3.6	Laboratory values			
14.3.6.1	Clinical Chemistry & Haematology	SAS	Descriptive Statistics	T3a
14.3.6.2	Clinical Chemistry & Haematology per category	SAS	Frequency Table (number and percentage of patients with normal values, abnormal values with clinical significance and abnormal values without clinical significance)	T4a
14.3.6.3	Change in Clinical Chemistry & Haematology	SAS	Shift Table	T14
14.3.7	Physical Examination			
14.3.7.1	Physical examination	SAS	Frequency table of patients with physical examination (yes/no)	T4

14.3.7.2	Abnormalities during physical examination	SAS	Frequency table of patients with abnormalities during physical examination	T4
16	Appendices			
16.2	Patient data listings			
16.2.1	Patient disposition	Enrolled Set	Individual patient data listing to analysis sets by cohort including reasons for exclusions, if applicable	L1
16.2.2	Violations of inclusion/exclusion criteria	Enrolled Set (only patients with violations)	Individual patient data listing by cohort	L6
16.2.3	Discontinuation	Enrolled Set	Individual patient data listing including reasons for discontinuation	L2
16.2.4	Demographic data / Informed Consent / Randomisation	Randomised Set	Individual patient data listing by cohort	L3
16.2.5	Vital Signs	FAS	Individual patient data listing by cohort and visit	L6
16.2.6.1	vIGA-AD TM score	Enrolled Set	Individual patient data listing by cohort and visit	L6
16.2.6.2	EASI score	Enrolled Set	Individual patient data listing by cohort and visit	L6
16.2.6.3	NRS score	Enrolled Set	Individual patient data listing by cohort and visit	L6
16.2.6.4	BSA	Enrolled Set	Individual patient data listing by cohort and visit	L6
16.2.6.5	SCORAD	Enrolled Set	Individual patient data listing by cohort and visit	L6
16.2.6.6	DLQI score	Enrolled Set	Individual patient data listing by cohort and visit	L6
16.2.6.7	POEM score	Enrolled Set	Individual patient data listing by cohort and visit	L6
16.2.6.8	AIS	Enrolled Set	Individual patient data listing by cohort and visit	L6
16.2.6.9	PO-SCORAD score	Enrolled Set	Individual patient data listing by cohort and visit	L6

16.2.7	Adverse Events Listings			
16.2.7.1	Adverse events	Enrolled Set	Individual patient data listing by cohort	L4
16.2.7.2	Serious adverse events	Enrolled Set	Individual patient data listing by cohort	L4
16.2.7.3	AEs related to DS107	Enrolled Set	Individual patient data listing by cohort	L4
16.2.7.4	AEs leading to death	Enrolled Set	Individual patient data listing by cohort	L4
16.2.7.5	AEs leading to study discontinuation	Enrolled Set	Individual patient data listing by cohort	L4
16.2.7.6	AEs before first administration of DS107	Enrolled Set	Individual patient data listing by cohort	L4
16.2.8	Listing of individual laboratory measurements			
16.2.8.1	Laboratory values	SAS	Individual patient data listing of laboratory results (haematology, clinical chemistry)	L5
16.2.8.2	Laboratory values outside the normal range	SAS	Individual patient data listing of laboratory results outside the normal range	L5
16.2.9	Other Listing			
16.2.9.1	Physical examinations	SAS	Individual patient data listing by cohort and visit	L6
16.2.9.2	Medical History / Concomitant diseases	FAS	Individual patient data listing by cohort	L6
16.2.9.3	Childbearing status and Pregnancy test data	FAS	Individual patient data listing by cohort and visit	L6
16.2.9.4	Virology	FAS	Individual patient data listing by cohort	L6
16.2.9.5	ECG	FAS	Individual patient data listing by cohort and visit	L6
16.2.9.6	Study drug dispensed	SAS	Individual patient data listing by cohort and visit	L6
16.2.9.7	Patient diary compliance	SAS	Individual patient data listing by cohort and visit	L6
16.2.9.8	IMP accountability and IMP compliance	SAS	Individual patient data listing by cohort and visit	L6
16.2.9.9	Previous and Concomitant medication	FAS	Individual patient data listing by cohort	L6

16.2.9.10	Violations of inclusion/exclusion criteria	Enrolled Set (only patients with violations)	Individual patient data listing by cohort	L6
16.2.9.11	Protocol violations	SAS	Individual patient data listing by cohort	L6

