	
For the purpose of efficacy analysis, patients who receive rescue treatment during the study treatment period will be considered treatment failures from the time rescue treatment is used.
 
Topical corticosteroids or calcineurin inhibitors may be used for rescue, but should be reserved for problem areas only, eg, face, neck, intertriginous and genital areas, etc. If a patient receives rescue treatment with systemic corticosteroids or non-steroidal systemic immunosuppressive drugs (cyclosporine, methotrexate, mycophenolate mofetil, azathioprine, etc.) study treatment will be immediately discontinued.
 
Investigators should make every attempt to conduct efficacy and safety assessments (eg, disease severity scores, safety labs) immediately before administering any rescue treatment.

STATISTICAL ANALYSIS	
The primary analysis will be conducted in the full analysis set (FAS) population.
 
A longitudinal mixed model for binary outcomes (GENMOD) will be used to separately analyze the binary primary and secondary efficacy endpoints at Week 16.
 
Change from baseline for secondary and exploratory endpoints (vIGA-ADTM, EASI, NRS, BSA, SCORAD, DLQI, POEM, AIS and PO-SCORAD) will be analysed using mixed model with repeated measures (MMRM). The models will include Treatment Arm as a factor and respective baseline value as a covariate, with the treatment-by-visit interaction term as a random effect to account for missing data at Week 16.
 
Sensitivity analyses will be performed to assess the robustness of the Missing at Random (MAR) assumptions that support the GENMOD methods above for imputing missing data.

SPONSOR:	DS Biopharma

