### 12.8.3 Secondary variables

IGA and EASI-75 responders at other time points will also be analysed using a GLMM model similar to that described in Section 12.8.2.

The efficacy variables and their changes from baseline will be summarized with descriptive statistics per treatment group and visit. This applies to the vIGA-AD™, EASI, NRS scores for pruritus, DLQI, POEM, SCORAD, AIS and PO-SCORAD. Change from baseline endpoints will be analysed using Mixed Model with Repeated Measures (MMRM) with Treatment Arm, Visit and Treatment x Visit Interaction as a factors and baseline value as a covariate, to account for missing data. The secondary efficacy analyses will be based on the FAS only. For vIGA-AD™ as a 5-level ordinal variable, mixed ordinal logistic regression will be used with factors defined as above and IGA at baseline as a factor too.

If rescue medication is used, the patient will be specified as a non-responder from the time the rescue is used

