### 7.3 Efficacy - Secondary Endpoints Evaluation

All secondary efficacy analyses will be performed as described in chapter 6.2 with the FAS only.

IGA and EASI-75 responders at other time points will also be analysed using a GLMM model similar to that described in Section 6.1.

The efficacy variables and their changes from baseline will be summarized with descriptive statistics per treatment group and visit. This applies to the vIGA-ADTM, EASI, NRS scores for

pruritus, DLQI, POEM, SCORAD, AIS and PO-SCORAD. Change from baseline endpoints will be analysed using Mixed Model with Repeated Measures (MMRM) with Treatment Arm, Visit and Treatment x Visit Interaction as a factors and baseline value as a covariate, to account for missing data. For vIGA-ADTM as a 5-level ordinal variable, mixed ordinal logistic regression will be used with factors defined as above and IGA at baseline as a factor too.

If rescue medication is used, the patient will be specified as a non-responder from the time the rescue is used.

The following parameters will be analysed as described above:

- Proportion of patients achieving a vIGA-ADTM score of 0 (clear) or 1 (almost clear) and a decrease of at least 2 points in vIGA-ADTM in treated population compared to placebo population from baseline to Week 4, 8, 12, 18 and 20
- Change in proportion of patients achieving a vIGA-ADTM score of 0 (clear) or 1 (almost clear) and a decrease of at least 2 points in vIGA-ADTM in treated population compared to placebo population from Week 16 to Week 18 and 20.
- Absolute proportion of patients achieving EASI-75 ( $\geq 75\%$  improvement from baseline) in treated population compared to placebo population at Week 4, 8, 12, 18 and 20
- Change from baseline in vIGA-ADTM score in treated population compared to placebo population to Week 4, 8, 12, 16, 18 and 20
- Change from Week 16 in vIGA-ADTM score in treated population compared to placebo population to Week 18 and 20.
- Change from baseline in EASI in treated population compared to placebo population to Week 4, 8, 12, 16, 18 and 20
- Change from Week 16 in EASI in treated population compared to placebo population to Week 18 and 20.

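### SAP section 8 labels three binary secondary outputs (EASI-50, itch NRS 4-point and 3-point response) as MMRM, which contradicts the protocol synopsis at Week 16 and lacks support in the text at the other weeks

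*SAP*

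**What the plan says.** **Protocol.** Section 5.2 defines EASI-50, a fall of at least 4 points in worst itch NRS, and a fall of at least 3 points as proportions of patients. Each is assessed at Weeks 4, 8, 12, 16, 18 and 20. The synopsis, under Statistical Analysis, states: "A longitudinal mixed model for binary outcomes (GENMOD) will be used to separately analyze the binary primary and secondary efficacy endpoints at Week 16". Its next paragraph gives MMRM to change-from-baseline endpoints. Section 12.8.3 adds: "IGA and EASI-75 responders at other time points will also be analysed using a GLMM model similar to that described in Section 12.8.2".

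**SAP text.** Section 7.3 repeats that sentence with its own cross-reference, "IGA and EASI-75 responders at other time points will also be analysed using a GLMM model similar to that described in Section 6.1", and then says: "Change from baseline endpoints will be analysed using Mixed Model with Repeated Measures (MMRM". It names no model for EASI-50 or NRS responders. It does promise p-values for both NRS responder endpoints at the six endpoint weeks.

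**SAP section 8.** Three rows carry the MMRM label with shells T8.1/T8.2:
- 14.2.2.2.4, "EASI-50 proportion from baseline to week 4, 8, 12, 16, 18, 20 (MMRM"
- 14.2.2.3.1, "NRS 4 point decrease proportion (MMRM"
- 14.2.2.3.2, "NRS 3 point decrease proportion (MMRM"

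The neighbouring EASI-75 row, 14.2.2.2.1, reads "EASI-75 proportion from baseline to week 4, 8, 12, 18, 20 (GLMM" and uses T6.1/T6.2. So does the vIGA-AD 0/1 row, 14.2.2.1.1.

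**The concern.** An MMRM is a Gaussian model for a continuous outcome, and here it is attached to 0/1 variables. For these three endpoints the section 8 label is the only place where the SAP names a model, so a programmer working from section 8 would fit it. At Week 16 that departs from the protocol.

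The model for a pre-specified secondary endpoint would then be settled by whichever document is followed, possibly after unblinding. EASI-50 and EASI-75 are two cut-offs of the same score, yet they would be analysed by different classes of model. The NRS responder p-values would come from a model that neither SAP 7.3 nor the protocol assigns to a responder endpoint.

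**Working it through.** **1. Passages side by side**

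| Source | Binary model assigned to | MMRM assigned to |
|---|---|---|
| Protocol synopsis | Binary primary and secondary endpoints, Week 16 | Change-from-baseline endpoints |
| Protocol 12.8.3 | IGA and EASI-75 responders, other time points | Change-from-baseline endpoints |
| SAP 7.3 | IGA and EASI-75 responders, other time points | Change-from-baseline endpoints |
| SAP 8 | vIGA-AD 0/1 and EASI-75 rows (T6.1/T6.2) | Change-score rows, and the EASI-50 and two NRS responder rows (T8.1/T8.2) |

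The synopsis sets its binary model against MMRM in adjacent paragraphs, so MMRM cannot be read as one form of that binary model.

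**2. Count**

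- Six secondary rows with a model label are responder proportions. 14.2.2.1.1, 14.2.2.1.2 and 14.2.2.2.1 carry GLMM; 14.2.2.2.4, 14.2.2.3.1 and 14.2.2.3.2 carry MMRM.
- Contradicted: 3 endpoints × Week 16 = 3 results.
- Label without support in the text: 3 endpoints × 5 other weeks = 15 results.
- NRS responder p-values promised: 2 endpoints × 6 weeks = 12, of which 2 (Week 16) are in direct conflict.
- For EASI-50, the row title and SAP 7.3 include Week 16. The row's content cell lists only Weeks 4, 8, 12, 18 and 20.

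**3. Sample size (background)**

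Inputs from protocol 12.3: 12% placebo, 15-point difference (so 27%), two-sided 5%, 80% power. The mean rate is 0.195.

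n = [1.960·√(2·0.195·0.805) + 0.842·√(0.12·0.88 + 0.27·0.73)]² / 0.15² = 108.3 per arm.

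The plan tabulates 108.4 and uses 110. Power at 110 is 0.806. The figure reproduces, and the labels do not affect it.

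**4. Illustration of what the label changes**

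The documents give no expected rates for the three endpoints, so three pairs are assumed. The first borrows the plan's vIGA-AD rates. The calculation takes 110 per arm, one visit, complete data, no covariate and a logit link.

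- Risk difference: SE = √[p0(1−p0)/n + p1(1−p1)/n]
- Log odds ratio: SE = √[1/(np0) + 1/(n(1−p0)) + 1/(np1) + 1/(n(1−p1))]

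| Assumed rates | Risk difference (SE) | z, p | Odds ratio (95% CI) | z, p |
|---|---|---|---|---|
| 12% vs 27% | 0.15 (0.0525) | 2.859, 0.0042 | 2.71 (1.33 to 5.53) | 2.744, 0.0061 |
| 30% vs 45% | 0.15 (0.0645) | 2.326, 0.020 | 1.91 (1.10 to 3.32) | 2.286, 0.022 |
| 50% vs 65% | 0.15 (0.0659) | 2.277, 0.023 | 1.86 (1.08 to 3.19) | 2.241, 0.025 |

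In this simplified setting the reported measure changes and the p-value hardly moves. Neither planned analysis is this simple: both are longitudinal and baseline-adjusted, and the GLMM has a patient random effect. With a logit link its odds ratio would be patient-specific. By the usual attenuation approximation, a marginal 2.71 corresponds to about 3.2 or 4.7 if the random-intercept SD is 1 or 2 (assumed values).

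**The case against.** The best defence is that little depends on these labels. A linear model for a 0/1 outcome is legitimate and gives a risk difference. Observed responder rates are tabulated separately (14.2.2.2.6 and 14.2.2.3.7). The documents give these secondary endpoints no share of alpha. SAP 7.3 also opens by pointing to the descriptive methods of 6.2. All of this limits the harm, and none of it removes the conflict. SAP 7.3 goes on to specify models and promises NRS p-values, so a test is planned and its model must be fixed.

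The defence is also right about several stronger readings that a reader might infer:

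- *The label contradicts the protocol at every visit.* The synopsis sentence covers Week 16 only. At the other five weeks section 8 does name a model, but one that the text reserves for another kind of endpoint.
- *The baseline covariate is undefined.* The synopsis gives the MMRM each endpoint's own baseline value, and SAP 6.1 gives the GLMM baseline vIGA-AD, including for EASI-75. Once the model is chosen, the baseline term follows.
- *Results will certainly appear as risk differences against odds ratios.* Neither document states a link or an effect measure for the GLMM, and the contents of T6.1/T6.2 and T8.1/T8.2 are not available. Different scales are plausible but not documented.
- *Significance would change, or would not.* The illustration models neither planned analysis and settles neither claim.

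**Conclusion.** The point holds as a conflict between protocol and SAP on three secondary endpoints. At Week 16 the MMRM label on EASI-50, NRS 4-point and NRS 3-point response contradicts the synopsis (three results). At the other five weeks the label has no basis in SAP 7.3 or protocol 12.8.3 (15 results). No other passage corrects it. All three rows carry both the MMRM label and the shells used for change scores, so this is more than one mistyped title, although the intended model cannot be confirmed without the shells.

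The impact is confined to the model and effect measure reported for these endpoints. The odds ratios and p-values above are illustrative only and rest on the assumptions stated with them. A reader might infer that the trial's main conclusion is exposed. It is not: both primary endpoints are assigned GLMM in SAP 6.1 and in section 8.

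The exploratory vIGA-AD 2-point outputs (14.2.2.6.1 and 14.2.2.6.2) are also labelled MMRM, but they are a consistency point only. The synopsis sentence does not cover exploratory endpoints, and SAP 7.4 can be read as the source of the label. Against that, the comparable secondary follow-up output, 14.2.2.1.2, uses GLMM.

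**What to change.** The change should be made before unblinding.

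1. In SAP 7.3, extend the GLMM sentence to EASI-50 and to the NRS 4-point and 3-point responders at all listed weeks, including Week 16. Use the SAP 6.1 model with baseline vIGA-AD as already specified there.
2. In SAP section 8, relabel 14.2.2.2.4, 14.2.2.3.1 and 14.2.2.3.2 as GLMM with shells T6.1/T6.2.
3. Add Week 16 to the content cell of 14.2.2.2.4.
4. For consistency, make the same change to 14.2.2.6.1 and 14.2.2.6.2, with a matching phrase in SAP 7.4.

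The cost is a sentence or two and a handful of table entries. No data collection, primary analysis or sample-size change is involved.
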